## 15 APPENDICES

### Appendix 1      Responsibilities of the Investigator

Clinical research trials sponsored by the Sponsor are subject to ICH GCP and all the applicable local laws and regulations.

The Investigator agrees to assume the following responsibilities:

1. Conduct the trial in accordance with the protocol ICH-E6 (R2), and all the applicable local laws and regulations.
2. Personally conduct or supervise the staff who will assist with the protocol.
3. Ensure that trial-related procedures including trial-specific (non-routine/non-standard panel) screening assessments are NOT performed on potential subjects, prior to the receipt of written approval from relevant governing bodies/authorities.
4. Ensure that all colleagues and employees assisting in the conduct of the trial are informed of these obligations.
5. Secure prior approval of the trial and any changes by an appropriate IEC and competent authority.
6. Ensure that the IEC will be responsible for initial review, continuing review, and approval of the protocol.
7. Ensure that requirements for informed consent, as outlined in ICH-E6 (R2) 4.8 and local regulations, are met.
8. Obtain valid informed consent from each subject and document the date of consent in the subject's medical chart. Valid informed consent is the most current version approved by the IEC. Each informed consent form should contain a subject authorization section that describes the uses and disclosures of a subject's personal information (including personal health information) that will take place in connection with the trial. If an informed consent form does not include such a subject authorization, then the Investigator must obtain a separate subject authorization form from each subject.
9. Prepare and maintain adequate case histories of all persons entered into the trial, including eCRFs, hospital records, laboratory results, etc., and maintain these data for a minimum of 2 years following notification by the Sponsor that all investigations have been discontinued or that the regulatory authority has approved the marketing application. The Investigator should contact and receive written approval from the Sponsor before disposing of any such documents.
10. Ensure that clinical data is entered into the eCRFs on the visit day during the staggered enrollment phase and within 5 days post-visit for all other visits.
11. Allow possible inspection and copying by the regulatory authority of GCP-specified source documents.
12. Maintain current records of the receipt, administration, and disposition of Sponsor-supplied vaccines, and return all unused Sponsor-supplied vaccines to the Sponsor.
13. In the event of an SAE, AESI or overdose notify the CRO within 24 hours via SAE/AESI/overdose/misuse report form signed by the Investigator.
14. Review and provide a signature as approval of the content of the clinical trial report (to be reported by the coordinating Investigator).

## **Appendix 2      Emergency Procedures**

During and after subjects' participation in this trial, the Investigator or institution should ensure that adequate medical care is provided to subjects who present with any AEs, including clinically significant laboratory values related to the administration of the trial vaccine. The Investigator or institution should inform subjects when medical care is needed for intercurrent illness(es) of which the Investigator becomes aware.

Emergency equipment for the immediate treatment of allergic/anaphylactic reactions (steroids, H1, H2 antihistaminergic agents, intravenous fluids, oxygen, epinephrine and equipment for cardiopulmonary resuscitation) must be available at all times for the treatment of these events, and trained personnel must be present at all times while subjects are being monitored after vaccination.

The trial site should have immediate access to equipment and appropriately qualified staff for resuscitating and stabilizing subjects in an acute emergency (such as cardiac emergencies, anaphylaxis, cytokine release syndrome, convulsions, hypotension), and ready availability of intensive care unit and other hospital facilities.

### **Appendix 3 Safety Laboratory Assessments**

The tests detailed in Table 6 will be performed by the local laboratory.

Additional tests may be performed at any time during the trial as determined necessary by the Investigator or required by local regulations.

**Table 6 Protocol-Required Safety Laboratory Assessments**

Laboratory Assessments	Parameters
Hematology	Complete blood count including differential and platelets
Clinical Chemistry/Biochemistry	Magnesium, creatinine, albumin and lactate dehydrogenase, C-reactive protein, gamma glutamyl transferase, blood urea nitrogen, bilirubin (direct/indirect), calcium, alkaline phosphatase, sodium, potassium, total protein, glutamic oxaloacetic transaminase/aspartate aminotransferase, glutamic pyruvic transaminase/alanine aminotransferase
Coagulation	Prothrombin time/international normalized ratio, activated partial thromboplastin time
Serum/Urine Pregnancy Tests	Human chorionic gonadotropin

The Investigator must document his review of each laboratory safety report, by signing and dating the report.

#### **Appendix 4 Case Definition for COVID-19**

According to CEPI's guidance "*COVID-19 Efficacy Endpoints in Interventional Trials: What Constitutes an Incident Clinical Disease Case and What Triggers Diagnostic Work-Up Version 2.0 dated 25 June 2020*", virologically-confirmed COVID-19 is defined as follows:

An RT-PCR confirmed an acute illness that is clinically consistent with COVID-19 based on the presence of at least 1 new-onset symptom: a) persistent cough, b) dyspnea or tachypnea (RR >20/min), c) low peripheral capillary oxygen saturation ( $\text{SpO}_2 <95\%$  on room air) as measured by pulse-oximetry, d) chest pain, e) radiographic findings consistent with LRTD, f) fever (defined as body temperature of  $\geq 37.8^\circ\text{C}$ , irrespective of method), g) myalgia, h) chills, i) loss of smell or taste, j) headache, k) sore throat, l) diarrhea.

There will likely be further updates to this guidance, and the Sponsor will take these into consideration during the course of the trial.

## **Appendix 5 Trial Governance Considerations**

CureVac AG is the Sponsor of this trial. PRA Health Sciences is the CRO appointed to coordinate the conduct of this trial.

## **Appendix 6      Protocol Changes**

Amendments to this trial protocol may be made following the procedures specified by local laws and regulations. Substantial amendments to this trial protocol may be implemented only if the approval of the competent authority/authorities [CA(s)] and a favorable opinion of the IEC(s) have been obtained.

Substantial amendments to the conduct of the clinical trial may arise from changes to the protocol or from new information relating to the scientific documents in support of the trial. Amendments to the trial are regarded as “substantial” where they are likely to have a significant impact on:

- The safety, physical health and mental integrity of the subjects.
- The scientific value of the trial.
- The conduct or management of the trial.
- The quality or safety of any medicinal product used in the trial.

If a new event occurs related to the conduct of the trial or the development of the investigational medicinal product, which may affect the safety of the subjects, the Sponsor and the Investigator will take appropriate safety measures to protect the subjects against any immediate hazard. The Sponsor will immediately inform the CA(s) and IEC(s) of the new events and the measures taken.

## Appendix 7 Potential Immune-Mediated Diseases

Current list of pIMDs:

### Gastrointestinal disorders:

- Celiac disease
- Crohn's disease
- Ulcerative colitis
- Ulcerative proctitis

### Liver disorders:

- Autoimmune cholangitis
- Autoimmune hepatitis
- Primary biliary cirrhosis
- Primary sclerosing cholangitis

### Metabolic diseases:

- Addison's disease
- Autoimmune thyroiditis (including Hashimoto thyroiditis)
- Diabetes mellitus type I
- Grave's or Basedow's disease

### Musculoskeletal disorders:

- Antisynthetase syndrome
- Dermatomyositis
- Juvenile chronic arthritis (including Still's disease)
- Mixed connective tissue disorder
- Polymyalgia rheumatic
- Polymyositis
- Psoriatic arthropathy
- Relapsing polychondritis
- Rheumatoid arthritis
- Scleroderma, including diffuse systemic form and CREST syndrome
- Spondyloarthritis, including ankylosing spondylitis, reactive arthritis (Reiter's Syndrome) and undifferentiated spondyloarthritis
- Systemic lupus erythematosus
- Systemic sclerosis

### Neuro-inflammatory disorders:

- Acute disseminated encephalomyelitis, including site specific variants (e.g., non-infectious encephalitis, encephalomyelitis, myelitis, myeloradiculomyelitis)
- Cranial nerve disorders, including paralyses/paresis (e.g., Bell's palsy)
- Guillain-Barré syndrome, including Miller Fisher syndrome and other variants
- Immune-mediated peripheral neuropathies, Parsonage-Turner syndrome and plexopathies, including chronic inflammatory demyelinating polyneuropathy, multifocal motor neuropathy, and polyneuropathies associated with monoclonal gammopathy
- Multiple sclerosis
- Narcolepsy
- Optic neuritis
- Transverse Myelitis

**Skin disorders:**

- Alopecia areata
- Autoimmune bullous skin diseases, including pemphigus, pemphigoid and dermatitis herpetiformis
- Cutaneous lupus erythematosus
- Erythema nodosum
- Morphea
- Lichen planus
- Psoriasis
- Sweet's syndrome
- Vitiligo

**Vasculitides:**

- Large vessels vasculitis including: giant cell arteritis such as Takayasu's arteritis and temporal arteritis
- Medium sized and/or small vessels vasculitis including: polyarteritis nodosa, Kawasaki's disease, microscopic polyangiitis, Wegener's granulomatosis, Churg-Strauss syndrome (allergic granulomatous angiitis), Buerger's disease thromboangiitis obliterans, necrotizing vasculitis and anti-neutrophil cytoplasmic antibody (ANCA) positive vasculitis (type unspecified), Henoch-Schonlein purpura, Behcet's syndrome, leukocytoclastic vasculitis

**Others:**

- Antiphospholipid syndrome
- Autoimmune hemolytic anemia
- Autoimmune glomerulonephritis (including immunoglobulin A nephropathy, glomerulonephritis rapidly progressive, membranous glomerulonephritis, membranoproliferative glomerulonephritis, and mesangioproliferative glomerulonephritis)
- Autoimmune myocarditis/cardiomyopathy
- Autoimmune thrombocytopenia
- Goodpasture syndrome
- Idiopathic pulmonary fibrosis
- Pernicious anemia
- Raynaud's phenomenon
- Sarcoidosis
- Sjögren's syndrome
- Stevens-Johnson syndrome
- Uveitis

## **Appendix 8 Adverse Events of Special Interest for SARS-CoV-2 Vaccines**

Current list of AESIs (based on Brighton Collaboration via CEPI's Safety Platform for Emergency vACCines [SPEAC] Project):

### **Immunological disorders:**

- Anaphylaxis
- Vasculitides
- Enhanced disease following immunization
- Multisystem inflammatory syndrome in children
- Subacute thyroiditis

### **Respiratory disorders:**

- Acute respiratory distress syndrome
- COVID-19

### **Cardiac disorders:**

Acute cardiac injury including:

- Microangiopathy
- Heart failure and cardiogenic shock
- Stress cardiomyopathy
- Coronary artery disease
- Arrhythmia
- Myocarditis, pericarditis

### **Hematological disorders:**

- Thrombocytopenia

### **Coagulation disorder:**

- Deep vein thrombosis
- Pulmonary embolus
- Cerebrovascular stroke
- Limb ischemia
- Hemorrhagic disease

### **Renal disorders:**

- Acute kidney injury

### **Gastrointestinal disorders**

- Liver injury
- Pancreatitis

### **Neurological disorders:**

- Generalized convulsion
- Guillain-Barré Syndrome
- Acute disseminated encephalomyelitis
- Anosmia, ageusia
- Meningoencephalitis

### **Dermatologic disorder:**

- Chilblain-like lesions
- Single organ cutaneous vasculitis
- Erythema multiforme

**Other:**

- Serious local/systemic adverse reaction following immunization
- Rhabdomyolysis

\*\* These are generally the conditions one encounters in normal subjects as AESI, but in this trial we use comorbid subjects and some of them may have coronary disease, arrhythmias or myocarditis to start with.

## Appendix 9 Adverse Events: Definitions and Procedures for Recording, Evaluating, Follow-up, and Reporting

### Definition of an Adverse Event (AE)

Definition of an AE:

• An AE is any untoward medical occurrence in a subject or clinical investigation subject administered a pharmaceutical product and which does not necessarily have to have a causal relationship with this treatment.

• An AE can therefore be any unfavorable and unintended sign (including an abnormal laboratory finding, for example), symptom, or disease temporally associated with the use of a medicinal product, whether or not considered related to the medicinal product.

• All AEs fall into 1 of 2 categories: “non-serious” or “serious”.

Examples of an AE include:

• Any abnormal laboratory test results (hematology, clinical chemistry, or urinalysis) or other safety assessments (e.g., ECG, radiological scans, vital signs measurements), including those that worsen from baseline, considered clinically significant in the medical and scientific judgment of the Investigator (i.e., not related to a known concomitant disease).

• Exacerbation of a chronic or intermittent pre-existing condition including either an increase in frequency and/or intensity of the condition.

• New conditions detected or diagnosed after administration of the trial vaccine even though it may have been present before the start of the trial.

• Signs, symptoms, or the clinical sequelae of a suspected drug-drug interaction.

• Signs, symptoms, or the clinical sequelae of a suspected overdose of either trial vaccine or a concomitant medication/vaccination.

• An adverse effect of the trial vaccine or concomitant medication/vaccination.

• An accident or injury.

Events NOT Meeting the AE Definition:


• Medical or surgical procedures or other therapeutic interventions themselves are not AEs, but the condition for which the surgery/intervention is required is an AE and should be documented accordingly.

• Planned surgical measures and the condition(s) leading to these measures are not AEs, if the condition(s) was (were) known before the period of observation (see below) and did not worsen during trial.

• In the latter case the condition should be reported as medical history.

• Situations where an untoward medical occurrence did not occur (e.g., social and/or convenience admission to a hospital).

• Anticipated day-to-day fluctuations of pre-existing disease(s) or condition(s) present or detected at the start of the trial that do not worsen.

 
Death is not considered an AE but an outcome.

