Risks from phlebotomy are well known and minimal. Venipuncture is a routine procedure the medical community commonly uses to obtain blood samples. Immediate complications may include slight pain during puncture of the skin and, rarely, dizziness and syncope. Additionally, a hematoma may result from the venipuncture, but this has minimal risk. Infection of the skin/soft tissue at the puncture site, vein, or blood stream can occur, but are very rare with venous blood draws. Subject monitoring and aseptic techniques, such as using sterile disposable blood collection apparatuses and adhering to standard medical precautions, reduce any risk to a minimum. The amount of blood to be taken for sampling will not be harmful to the subject's health.

CVnCoV has not been investigated in an adult population with co-morbidities known to increase the risk for (severe) COVID-19. The safety and reactogenicity as well as immunogenicity of CVnCoV in this population will be investigated in the current trial.

The current trial is designed to observe if these comorbid subjects have additional risks to vaccination to assess risk-benefit ratio.

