#### **9.1.3 Safety Laboratory Assessments**

Blood samples for determination of hematology (complete blood count, including differential and platelets), clinical biochemistry, and coagulation will be analyzed as indicated in Table 1 in the first 50 subjects enrolled and vaccinated from each co-morbidity condition. Blood samples on Day 1 and Day 29 must be collected prior to vaccination. An overview of the safety laboratory tests is provided in Appendix 3.

In addition, a blood sample for serum pregnancy testing will be taken from women of childbearing potential to establish eligibility at screening. Urine pregnancy tests will be performed before each vaccination, unless the serum pregnancy test was performed less than 3 days before and yielded a negative result.

Laboratory data will be graded according with the United States Food and Drug Administration (US FDA) toxicity grading scale [27]. Any institutional normal reference ranges should be provided to demonstrate that they are appropriate.

A laboratory abnormality is however only considered an AE if considered clinically significant in the medical and scientific judgment of the Investigator.

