#### **9.1.5 Medical and Surgical History**

All significant findings and pre-existing conditions present in a subject prior to enrollment must be reported on the relevant medical history/current medical conditions screen of the eCRF.

Any changes in severity of the underlying condition will be monitored. Increases in severity meeting the definition of an SAE and considered to be related to the trial vaccine will be reported as a SUSAR (see Appendix 9).

Information should be provided on medical and surgical history and concomitant medical conditions specifying those ongoing on Day -7.

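### The Appendix 9 gloss on clinical significance lets an isolated laboratory worsening attributed to a studied co-morbidity go unrecorded as an adverse event

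*Protocol*

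**What the plan says.** Appendix 9 of the protocol opens broadly. An AE is any unfavourable sign, symptom or disease, abnormal laboratory findings included, "whether or not considered related to the medicinal product". Under the line "Examples of an AE include", the first item takes abnormal laboratory tests and other safety assessments (ECG, radiology, vital signs), including those that worsen from baseline, where they are "considered clinically significant in the medical and scientific judgment of the Investigator (i.e., not related to a known concomitant disease"; the parenthesis closes there. The next item is "Exacerbation of a chronic or intermittent pre-existing condition including either an increase in frequency and/or intensity of the condition".

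Section 9.1.3 is stricter for laboratory values: "A laboratory abnormality is however only considered an AE if considered clinically significant in the medical and scientific judgment of the Investigator". It does not explain clinical significance. The SAE definition in Appendix 9 adds that an event outside the AE definition cannot be an SAE, whatever its consequences.

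Four other places bear on the point:
- The Appendix 9 list of events that are not AEs includes "Anticipated day-to-day fluctuations of pre-existing disease(s) or condition(s) present or detected at the start of the trial that do not worsen".
- Section 9.1.5 says "Any changes in severity of the underlying condition will be monitored". Its next sentence sends vaccine-related increases in severity that meet the SAE definition to SUSAR reporting.
- The causality section of Appendix 9 names underlying disease among the alternative causes the investigator weighs.
- Section 3.3.1 states the purpose: "The current trial is designed to observe if these comorbid subjects have additional risks to vaccination to assess risk-benefit ratio".

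**The concern.** The gloss puts a judgement about cause inside the test of whether an AE exists. In healthy volunteers that would rarely matter. Here each subject was enrolled because of a known disease, so a disease-based explanation is available for many of the findings of most interest: creatinine in chronic kidney disease or after renal transplant, blood pressure in hypertension.

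The trial has one arm, and the protocol says subjects act as their own control. Worsening from baseline is therefore the natural signal. If one site follows the gloss and another follows the exacerbation item, the same change is an AE at one and not at the other. What is at stake is the occurrence of unsolicited AEs within 28 days of each dose, a primary safety endpoint (Section 4.2.1), and the AE tables kept in the abbreviated scope (SAP Appendix 4).

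**Working it through.** No planned figure takes this definition as an input, so the check is a comparison of texts.

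1. **Reach of the gloss.** It is worded as an equivalence, and the sentence expressly includes worsening from baseline. The protocol offers no other explanation of clinical significance for laboratory, ECG or vital-sign results.

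2. **Laboratory values.** Section 9.1.3: a laboratory abnormality is an AE only if clinically significant. Appendix 9: clinically significant means not due to a known disease. Together, a laboratory worsening attributed to the known disease is not an AE. By the SAE rule it then cannot be an SAE.

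3. **ECG and vital signs.** No sentence makes clinical significance a necessary condition for these. Only the gloss in the example applies, so exclusion is an inference.

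4. **One finding under each passage.** Take a creatinine rise from baseline in a subject with chronic kidney disease, attributed to that disease.

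| Passage | Result |
|---|---|
| Appendix 9, general definition | AE |
| Appendix 9, first example, with its gloss | Does not qualify as an AE |
| Appendix 9, next example | AE, if read as increased intensity of the disease |
| Appendix 9, list of non-AEs | Not excluded, because it worsened |
| Section 9.1.3 | Depends on whether the gloss is applied |
| Section 9.1.5 | Change in severity monitored; the SUSAR route presupposes an AE |
| Appendix 9, causality | Disease weighed as a cause of an event already recorded |

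5. **Who is exposed.** Inclusion criterion 1 requires a studied co-morbidity, so all 129 enrolled subjects (SAP Section 6.3) have one. Safety laboratory tests are limited to the first 50 subjects per co-morbidity; vital signs are taken in everyone. The only scheduled ECG is at screening.

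6. **What else would show the finding.** Acute kidney injury, heart failure, coronary artery disease and arrhythmia are AESIs (protocol Appendix 8). Section 9.1.1.3 frames these listed AESIs as AEs, so an isolated value not accepted as an AE may not reach that list. Laboratory and vital-sign values are summarised with change from baseline and listed, and ECGs are listed (protocol Section 10.3.5.1; SAP Sections 12.7.4 to 12.7.6). Laboratory shift tables use reference-range categories, so a subject already high at baseline cannot shift upward. These outputs carry no causality assessment.

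7. **Scale.** The documents give no rate of such findings and no split of the 129 by co-morbidity. As arithmetic only, one subject missing from a preferred-term row changes the overall percentage by 1/129 = 0.8 points. With an even split (assumption), 129/7 = 18.4 per co-morbidity and 1/18.4 = 5.4 points. In a stratum of 25 it is 1/25 = 4.0 points, and in one of 50 it is 1/50 = 2.0 points. This shows how sensitive the tables are. It does not estimate how many events are missed.

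**The case against.** A reader might infer that the plan excludes worsening of the co-morbidities from AE recording. The documents do not support that. The glossed sentence is one item in a list of examples and contains no exclusion. The general definition is broad, the next item makes exacerbation an AE, and the non-AE list removes only fluctuations without worsening. Section 9.1.5 also assumes that worsening is reported. The necessary-condition wording is in Section 9.1.3, which covers laboratory values alone and does not repeat the gloss.

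A reader might also infer that AESI diagnoses such as acute kidney injury or arrhythmia are filtered out, or that AE rates are biased low as a matter of fact. Neither is shown. The footnote to Appendix 8 recognises that some subjects enter with coronary disease or arrhythmias, yet those terms stay on the list. Investigators are told to record a diagnosis in preference to isolated signs where possible. No document describes site practice. The ECG route is thin, since later ECGs are done only when clinically indicated and a new finding would usually come with a clinical work-up.

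It can fairly be added that the analysis is descriptive, that enrolment stopped at 129 and that the Grade 3 adverse-reaction analysis was dropped (SAP Section 6.4), so no decision rule turns on this clause.

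All of that stands and narrows the point. It does not remove the conflict: for an isolated laboratory change judged neither an exacerbation nor an AESI, the text supports opposite answers.

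**Conclusion.** The concern holds as an internal inconsistency with a definite gap. An isolated laboratory worsening attributed to the studied co-morbidity can, on a direct reading of Section 9.1.3 with Appendix 9, be left unrecorded as an AE and hence as an SAE. For vital signs and ECG the same outcome is only an inference from the gloss.

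Unsolicited AE occurrence may therefore be under-recorded, and differently by site. Clinically evident exacerbations and listed AESI diagnoses should still be captured, and the underlying values stay visible in summaries or listings. The number of events affected cannot be derived from the documents. The conclusion assumes only that some investigators would apply the parenthesis as written. It merits correction because it touches a primary safety endpoint and costs little.

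**What to change.** Delete the parenthetical gloss in the first Appendix 9 example. Alternatively, reconcile it with the exacerbation item, the non-AE list and Sections 9.1.3 and 9.1.5. Either way, worsening from baseline that the investigator judges clinically significant should be an AE whatever its cause, with attribution to underlying disease handled in the causality assessment. Notify sites of the clarification.

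Before database lock, query only post-vaccination laboratory and vital-sign values whose toxicity grade worsened from baseline and which have no matching AE. The plan states toxicity grading for laboratory data (Section 9.1.3; SAP Section 12.7.4), so the grading to be used for vital signs must be specified first. Querying every value that moved in the wrong direction would be too broad: it would pull in ordinary measurement variation and bypass the clinical-significance standard.

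Cost: a one-line correction or site letter, one small round of queries across 129 subjects, and somewhat higher AE counts.
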